3.2.2. Secondary Endpoints

- Plasma PK parameters (AUC0-t, AUC0-5, Cmax and Tmax) will be calculated at Week 4. The PK parameters AUC0-5 and Cmax will be calculated using standard formulas inserting the lower limit of quantification (LLOQ) for non-quantifiable levels of the analyte; therefore, AUC0-5 will be an upper limit in case at least one time-point shows a non-quantifiable level of the analyte, and Cmax will be an upper limit in case all time points show non quantifiable levels of the analyte. For a given analyte, the PK parameters AUC0-t and Tmax will be calculated if at least one time-point shows a quantifiable level of the analyte. The PK parameters will be summarised using appropriate descriptive statistics including median, lower and upper quartiles, minimum and maximum.

Blood samples for PK assessments will be collected at

- SV2 (baseline sample)
- Week 2 (single time point before application of IP)
- Week 4; before application of IP and then at 1, 3, and 5 hours after the application.
- Week 8; (single time point. Subject should not apply IP on the day of the Week 8 visit)

The samples will be assayed for concentrations of the active ingredients (BDP and CAL) and for their main metabolites; MC1080 and betamethasone 17-propionate, respectively.

3.2.3. Safety Endpoints

- Adverse events (AEs) and serious adverse events (SAEs);
- Local skin reaction;
- Changes in safety laboratory test results;
- Changes in ECGs;
- Changes in vital signs and physical examinations.

3.2.4. Other Endpoints

- The proportion of subjects with treatment success, defined as a minimum 2-point decrease from baseline in the PGA on the body (trunk and/or limbs), and with or without scalp at Week 4 and Week 8.

**MC2-01-C6_STATISTICAL ANALYSIS PLAN_Final 3.0_07 September 2020**

- Subject assessment of treatment convenience at Week 8 using a Psoriasis Treatment Convenience Scale.

4. Study Design

4.1. General Study Design and Plan¹

This is a phase 2, open-label, single-group, multicentre trial in which the investigational product (IP), MC2-01 cream, is investigated in adolescent subjects (age 12 to 16 years, 11 months) with clinically diagnosed extensive psoriasis vulgaris of at least moderate disease severity (according to the Physician's Global Assessment of Disease Severity; PGA) on body (trunk and/or limbs), and with or without scalp involvement.

After written informed assent is provided by the subject and written informed consent is provided by the parent(s) or legal guardian(s) and the consent document is signed by the investigator or designee the subjects will undergo screening procedures. For subjects requiring a washout period, informed assent/informed consent must be completed prior to washout. Prior to Screening Visit 2 (SV2) the subject (or the parent(s) or legal guardian(s)) is instructed to keep a diary for a 4-day registration of the daily intake of calcium-rich nutrients. At SV2, a second morning urine sample will be collected at the site for analysis of the urinary calcium excretion. Subjects will have their HPA axis function assessed and a baseline PK sample is collected along with other baseline assessments to confirm the subject's eligibility before Day 0/Visit 1.

Subjects who fulfil all inclusion and exclusion criteria at Day 0/Visit 1 are enrolled in the trial and will apply one dose of trial medication topically once daily for 8 weeks.

[figure not shown]
Please refer to Figure 1 for an overview of the trial design.

Trial subjects will be enrolled at approximately 12 sites in Europe.

At Week 4 and Week 8, the effect of once-daily use of MC2-01 cream on the HPA axis and the calcium metabolism will be evaluated. Other assessments (local skin reactions, AEs, laboratory tests, electrocardiogram (ECG), vital signs and physical examination) and efficacy assessments are also performed. At Week 4, the PK profile of calcipotriol (CAL), betamethasone dipropionate (BDP) and their main metabolites MC1080 and betamethasone 17-propionate, respectively, will be assessed.

Figure 1

¹ This section is based on the sections 4.1 "Overall Trial Design".

**MC2-01-C6_STATISTICAL ANALYSIS PLAN_Final 3.0_07 September 2020**

*There should be at least four days between SV1 and SV2 in order to keep the food diary for 4 days prior to SV2.

The maximum trial duration for each subject will be approximately 18 weeks and includes a screening period of up to 6 weeks (if washout of medication is required), a treatment period of 8 weeks, and a follow-up period of up to 4 weeks. After Week 8 (Visit 5) a follow-up visit is required for all subjects. The end of trial is defined as last subject last visit.

Table 1 Schedule of Activities

MC2-01-C6_STATISTICAL ANALYSIS PLAN_Final 3.0_07 September 2020

| | SV 1 ^a | SV 2 | Visit 1 | Visit 2 | Visit 3 | Visit 4 | Visit 5 | Follow-up Visit ^b |
|---|---------------------|---------------|----------|------------|------------|---------------------------|------------|------------------------------|
| | | | Day 0 | Week 2 | Week 4 | Week 6 | Week 8 | FU |
| Examination | Day - 42 to Day - 8 | Day -7 to - 4 | Day 0 | Day 14 ± 2 | Day 28 ± 2 | Day 42 ± 2 | Day 56 ± 2 | Day 70-84 ± 2 |
| Informed assent/Informed consent ^c | X | | | | | | | |
| Inclusion/exclusion criteria | (X) | | X | | | | | |
| Urine pregnancy test ^d | X | | X | | | | | |
| Serum pregnancy test ^d | | X | | | X | | X | |
| Demographics, medical history | X | | | | | | | |
| Prior and concomitant medication | X | X | X | X | X | X | X | |
| Physical examination | X | | X | | X | | X | X |
| PGA | (X) | (X) | X | X | X | X | X | |
| Body Surface Area (BSA) involvement | (X) | (X) | X | | X | | X | |
| Vital signs | | | X | X | X | X | X | |
| Laboratory assessments | | X | | | X | (X) ^e | X | (X) |
| ACTH challenge test ^f | | X | | | X | | X | (X) |
| Morning urine assessment (second morning urine) | Instruct | X | | Instruct | Instruct X | Instruct (X) ^g | Instruct X | (X) |
| Review food diary | Instruct | X | | Instruct | Instruct X | Instruct (X) ^g | Instruct X | (X) |
| PK pre-dose blood sample (Single) | | X | Instruct | X | | Instruct | X | |
| PK serial blood samples ^h | | | | Instruct | X | | | |
| 12-Lead ECG | | X | | | X | | X | |
| Psoriasis Treatment Convenience Scale | | | | X | X | | X | |
| Dispense IP and diary for compliance | | | X | X | X | X | | |
| Collect IP | | | | X | X | X | X | |
| Compliance | | | | X | X | X | X | |
| Adverse event(s) ⁱ | | X | X | X | X | X | X | X |
| Local Skin Reactions | | | X | X | X | X | X | |

- a) A washout period of up to 6 weeks must be completed if the subject has been treated with anti-psoriatic treatments or other relevant medication, as defined by exclusion criteria.

There should be at least four days between SV1 and SV2 in order to keep the food diary for 4 days prior to SV2. Items denoted in [brackets] must be reviewed during screening, to assess if the subject is otherwise eligible. Such items must be checked for any change in eligibility status at Visit 1/Day 0 after the washout is completed.

- b) Follow-up visit is required 2 weeks after the Week 8 visit. For subject with HPA axis suppression at Week 8 the follow-up visit should be 4 weeks after the Week 8 visit.

If the albumin-corrected serum calcium or the urinary calcium creatinine ratio is elevated at Week 8 a repeat test should be performed. In case of a repeat of the urinary calcium creatinine ratio the subject should be instructed to record the calcium intact 4 days prior to the visit.

For Czech Republic and Hungary: if an on-site visit is not required the follow up visit can be a telephone call 2 weeks after Week 8 to ask for the wellbeing of the subject.

In addition, subjects discontinued due to a treatment-related AE will be monitored until the AE is resolved or until the medical condition of the subject is stable.

- c) Written informed assent must be provided by the subject and written informed consent must be provided by the parent(s), legal guardian(s) and the consent documents signed by the investigator or designee before any trial related procedures are carried out. For subjects requiring a washout period, informed assent/informed consent must be completed prior to washout.
- d) All female subjects.
- e) If serum albumin-corrected serum calcium is above the reference range at Week 4 a repeat test should be performed at Week 6.
- f) The ACTH challenge test must be performed between 7 and 9 AM, before IP application.
- g) If the urinary calcium: creatinine ratio is above the reference range at Week 4, a repeat test should be performed, and the food diary filled in at Week 6. If the repeat test is also above the reference range, 24-hour urine collection must be performed.
- h) Blood samples for PK analysis are drawn before IP application (pre-dose sample) and 1, 3, and 5 hours after IP application.
- i) AEs are to be collected from the date of signing informed assent/informed consent and first trial-related activity is performed.

4.2. Randomization and Blinding²

This is an open-label trial. All subjects who fulfil the trial eligibility requirements will be assigned to treatment with MC2-01. Neither randomization nor blinding will be performed.

² This section is based on the section 6.5 “Assignment to Treatment” of clinical study Protocol.

**MC2-01-C6_STATISTICAL ANALYSIS PLAN_Final 3.0_07 September 2020****5. Sample Size³**

It is planned to enroll approximately 30 subjects. The choice of sample size in this trial is based on regulatory considerations with respect to common practice in maximum use studies. For the PK population, the aim is to have at least 20 subjects included that have at least completed Week 4 (Visit 3).

The choice of sample size in this trial is not based on statistical considerations, but rather on regulatory considerations with respect to common practice in maximum use studies evaluating pharmacokinetic profiles and evidence of HPA safety.

6. General Considerations***6.1. Timing of Analyses***

One interim analysis following study completion by 7 treated subjects will be prepared.

The final analysis will be prepared in case the MC2-01-C6 is re-activated (refer to Section 6.4).

6.2. Analysis Populations

The main subject samples of interest are defined as follows.

The 'All enrolled subjects': all subjects for whom Informed Consent/Assent were obtained:

The 'Allocated to treatment': all subjects for whom Informed Consent/Assent were obtained and who had successfully completed Screening procedures and to whom any amount of trial medication was dispensed.

The 'Safety population': all subjects who are enrolled in the trial and dispensed the trial medication at Visit 1/Day 0, excluding subjects who return all of the trial medication unused. The Safety population will be used for all safety analyses other than evaluation of the HPA-axis.

The 'PK population': all subjects in the Safety population who have received the planned application of treatment at the Week 4 visit and have had at least one blood draw for PK assessment at Week 4.

The 'HPA population': all subjects in the Safety population that show normal HPA function at SV2:

- Serum cortisol concentration above 4.5mcg/dl (160nmol/l) before ACTH-challenge and equal or above 18 mcg/dl (500 nmol/l) 30 minutes after ACTH challenge, at SV2.

The HPA population will be used for the HPA axis suppression analysis.

³ This section is based on the section 5.1 "Subject Population" and 8.2 "Sample Size and Power Considerations" of clinical study Protocol.

**MC2-01-C6_STATISTICAL ANALYSIS PLAN_Final 3.0_07 September 2020**

For interim analyses *Interim* <Population Name> will be used for reporting.

6.3. Missing Data

No imputation will be made for missing data apart from missing or partial adverse event start date and concomitant medication end date necessary to calculate the treatment-emergent and prior/concomitant/post-treatment flags, correspondingly.

If the information about end date for prior/concomitant therapy is missing or incomplete, the following rules (Table 2.1.1 and Table 2.1.2) will be used for the classification of therapy as prior, concomitant or post-treatment.

Table 2.1.1 Management of partial and missing prior/concomitant therapy start date.

| Day | Month | Year | Processing |
|------------|--------------|-------------|---|
| is missing | is known | is known | Therapy will be classified as post-treatment, if start month and year > month and year of the last IMP dose, else – as prior or concomitant according to the definition and Table 2.1.2 |
| is missing | is missing | is known | Therapy will be classified as post-treatment, if start year > year of the last IMP dose, else – as prior or concomitant according to the definition and Table 2.1.2 |
| is missing | is known | is missing | Therapy will be classified as prior or concomitant according to the definition and Table 2.1.2 |
| is known | is missing | is missing | |
| is missing | is missing | is missing | |

Table 2.1.2 Management of partial and missing prior/concomitant therapy end date.

| Day | Month | Year | Processing |
|------------|--------------|-------------|--|
| is missing | is known | is known | Therapy will be classified as prior, if end month and year < month and year of the first IMP dose, else – as concomitant |
| is missing | is missing | is known | Therapy will be classified as prior, if end year < year of the first IMP dose, else – as concomitant |
| is known | is missing | is known | |
| is missing | is known | is missing | Therapy will be classified as concomitant |
| is known | is missing | is missing | |
| is missing | is missing | is missing | |

The medical history records will be categorized in prior/concurrent categories in a similar way.

**MC2-01-C6_STATISTICAL ANALYSIS PLAN_Final 3.0_07 September 2020**

If the information about adverse event start date and time is missing or incomplete, the following rules (Table 2.2) will be used for the classification of adverse events as TEAEs and non-TEAEs (occurred before the start of study treatment) and for identification of TEAEs occurred up to Week 4.

Table 2.2 Management of partial and missing AE start date.

| Day | Month | Year | TEAE flag | Occurrence up to Week 4 |
|------------|------------|------------|---|--|
| is missing | is known | is known | AE will be classified as TEAE, if month and year \geq month and year of the first dose of study therapy | TEAE will be classified as occurring up to Week 4, if month and year \leq month and year of the Visit 3 / Week 4 or subject discontinued before Visit 3 / Week 4 |
| is missing | is missing | is known | AE will be classified as TEAE, if year \geq year of the first dose of study therapy | TEAE will be classified as occurring up to Week 4, if year \leq year of the Visit 3 / Week 4 or subject discontinued before Visit 3 / Week 4 |
| is known | is missing | is known | | |
| is missing | is known | is missing | AE will be classified as TEAE | TEAE will be classified as occurring up to Week 4 |
| is known | is missing | is missing | | |
| is missing | is missing | is missing | | |

Original dates (without imputation) will be used for data listings.

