6.2 Dosing Regimen

Subjects are to apply the IP topically once daily, preferably in the evening, for 8 weeks. The subject should apply enough IP to treat the entire affected areas and rub in gently to ensure that the plaques are saturated with the medication. Up to 3 tubes of 60 gram will be dispensed for a treatment period of two weeks including the allowed visit window of 2 days.

The IP is applied to affected areas on the:

- scalp
- trunk (including the neck)
- limbs
 - arms (including the back of the hands)
 - legs (including the buttocks and the top of the feet).

Only affected areas are to be treated. The subjects should therefore not continue treatment on a skin area which has been cleared but treatment may be restarted in case of recurrence at the subjects discretion (Section 6.3).

The face, genitals, and intertriginous areas should not be treated with the IP. The first application is done at Day 0 under the supervision and instruction of the trial staff. Subsequent applications will be applied by the subject or by the parent(s) or legal guardian(s).

All subjects are instructed to apply IP in the morning on the day before the Week 2, Week 4 and Week 8 visits. On the day of these visits, the subjects should not apply any IP before the visit.

Subjects are to record the date and time of application in the subject dosing diary (with the assistance of the parent(s) or legal guardian(s), as needed). The treated area should not exceed 30% of the BSA.

In case an AE reported in one area of the body lead the investigator to the decision to discontinue treatment this will apply for treatment in general and not only to the area for which the AE was reported.

Detailed application instructions will be provided in the subject instructions.

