8.8.3 Adverse events

Adverse events will be coded using Medical Dictionary for Regulatory Activities (MedDRA) terminology. Treatment-emergent AEs will be summarised by the overall incidence of at least one event, incidence by body system, and incidence by body system and preferred term. Each subject

will contribute only once (e.g., the first occurrence) to each of the rates, regardless of the number of occurrences (events) the subject experiences. Treatment-emergent AEs will be summarised by severity (mild, moderate, or severe), and by relationship to trial product (none, unlikely, possible, probable, or definite). An AE is treatment-emergent if its date of onset is Day 1 (Baseline) or later.

Discontinuations from the trial due to AEs and SAEs will be listed by subject.

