**MC2-01-C6_STATISTICAL ANALYSIS PLAN_Final 3.0_07 September 2020**

dose of study therapy or is ongoing at the end of clinical study, then the condition/diagnosis will be classified as Concurrent. If the information about stop date of condition/diagnosis is missing or incomplete, the rules from section 6.3 will be applied for classification. Medical history record will be assumed to be Concurrent, unless there is clear evidence (through comparison of partial dates) to suggest that the condition/diagnosis stopped prior to the first dose of study therapy. If there is clear evidence to suggest that the condition/diagnosis stopped prior to the first dose of study therapy, the condition/diagnosis will be assumed to be Prior.

All data will be listed.

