**MC2-01-C6_STATISTICAL ANALYSIS PLAN_Final 3.0_07 September 2020**

severity (mild, moderate, or severe), and by relationship to trial product (none, possible, probable, or definite). An AE is treatment-emergent if its date of onset is on or after the date of the first application of the IP.

Only treatment emergent AEs will be summarized. In the listings, however, all occurrences of the AEs will be presented.

Number (percentage) of subjects and number of AEs will be presented for the Safety population in the following tables:

- All treatment-emergent AE / SAE;
- Treatment-emergent AE / SAE related to the study drug (relationship to trial product assessed by the investigator as possible, probable, or definite including those events where assessment is missing);
- TEAE by maximum severity;
- TEAE by closest relationship to study drug;
- TEAE related to study drug by maximum severity;
- TEAE related to cosyntropin;
- TEAE related to study procedures;
- TEAE leading to the permanent discontinuation of study drug (Action taken with IP=“Drug withdrawn”);
- TEAE leading to withdrawal (Did subject withdraw due to this AE? = “Yes”);
- TEAE leading to death (Outcome = “Death”);
- Non-serious TEAEs that occurred at a frequency of $\geq 5\%$ (if no events occurred at the 5% threshold all non-serious TEAEs will be tabulated).

This set of tables will be repeated for the adverse events occurring up to Visit 3 / Week 4. Treatment-emergent adverse events with start dates on or prior to Visit 3 / Week 4 date will be summarized separately. If subject discontinued from the study prior to Visit 3 / Week 4 his/her adverse events will also be included in these summaries. If subject missed Visit 3 / Week 4 the planned date of visit (study day) will be used to subset the events occurring up to Week 4.

Tables of TEAEs by maximum severity (closest relationship to study drug) will be prepared using the following rules: each SOC / PT category will include only the AEs with the worst severity (closest relationship) for each subject. In the Overall category, all AEs of the subjects will be presented. Each subject will be counted only once with the worst severity (closest relationship) in each SOC and each PT level as well as in the Overall level.

In case if severity or relationship to study drug is missing, the worst case value will be assumed and used in the summary.

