**MC2-01-C6_STATISTICAL ANALYSIS PLAN_Final 3.0_07 September 2020**
APPENDIX 1 TFLs Shells**Safety Analyses****Adverse Events**MC2 Therapeutics
MC2-01-C6**Table 14.3.1.1 Overall Summary of TEAEs**
Safety population
Page X of X

| | Total (N = XX) n (%) / E |
|---|--------------------------------|
| Any TEAE | XX (XX.X) / XX |
| Any TEAE related to study treatment | XX (XX.X) / XX |
| Any TEAE related to study procedures | XX (XX.X) / XX |
| Any TEAE related to Cosyntropin | XX (XX.X) / XX |
| Any Serious TEAE | XX (XX.X) / XX |
| Any Serious TEAE related to study treatment | XX (XX.X) / XX |
| Any TEAE leading to study treatment discontinuation | XX (XX.X) / XX |
| Any TEAE leading to withdrawal | XX (XX.X) / XX |
| Maximum Severity | |
| Mild | XX (XX.X) |
| Moderate | XX (XX.X) |
| Severe | XX (XX.X) |
| Strongest Causal Relationship to Study Treatment | |
| Not related | XX (XX.X) |
| Possibly related | XX (XX.X) |
| Probably related | XX (XX.X) |
| Definitely related | XX (XX.X) |

AE=Adverse Event; TEAE=Treatment-Emergent Adverse Event.

N: the number of subjects in the Safety population.

n: the number of subjects with at least one TEAE within a specific category. Percentages are calculated as $(100 \times n/N)$.

E: total number of TEAEs reported within a specific category.

A TEAE is defined as an AE that started after the first dose of the study treatment.

If the severity is missing for a TEAE, then 'Severe' category is assigned.

If the relationship is missing for a TEAE, then 'Definitely related' category is assigned.

MC2-01-C6_STATISTICAL ANALYSIS PLAN_Final 3.0_07 September 2020

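### SAP Table 2.2 can flag an adverse event as treatment-emergent although its recorded end date precedes the first application; the TEAE wording also differs for Day 0 events

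*SAP*

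**What the plan says.** **Incomplete start dates.** SAP 6.3 introduces Table 2.2 as serving the "classification of adverse events as TEAEs and non-TEAEs (occurred before the start of study treatment"). Its rows use only what is known of the start date:

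- Day missing: "AE will be classified as TEAE, if month and year" of onset are at or after those of the first dose.
- Month missing, year known: "AE will be classified as TEAE, if year" of onset is at or after the first-dose year.
- Year missing: always a TEAE.

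No row mentions the end date. Protocol 7.10.1 has the stop date of every AE recorded, and protocol 7.10.2 starts AE collection at consent or assent. SV1 may be as early as Day -42 and SV2 falls on Day -7 to -4 (protocol Table 7-1).

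Elsewhere the SAP does look at end dates. A medical history record (SAP 7.4) is taken as concurrent "unless there is clear evidence (through comparison of partial dates) to suggest that the condition/diagnosis stopped prior to the first dose of study therapy". SAP 7.5 and Table 2.1.2 treat medications in a similar way.

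**Definition of a TEAE.**

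- SAP 9.2: "An AE is treatment-emergent if its date of onset is on or after the date of the first application of the IP".
- SAP Appendix 1, Table 14.3.1.1 footnote: "A TEAE is defined as an AE that started after the first dose of the study treatment". The footnotes to Listings 16.2.7.1 to 16.2.7.4 likewise require a start after therapy was initiated.
- Protocol 8.8.3: "An AE is treatment-emergent if its date of onset is Day 1 (Baseline) or later". Protocol 6.2 states: "The first application is done at Day 0 under the supervision and instruction of the trial staff".

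SAP 14 does not mention the TEAE definition.

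**The concern.** SAP 9.2 summarises only TEAEs, so the flag decides what enters every AE table. Events before dosing are to be expected: collection starts at consent, and SV2 includes blood sampling and an intravenous cosyntropin test. The SAP plans separate tables of TEAEs related to cosyntropin and to study procedures. A reaction at SV2 that had resolved before any cream was applied could therefore be reported there as treatment-emergent if its start day was not recorded.

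The definitions raise a smaller issue. If the flag is programmed from SAP 9.2, the printed footnotes describe a slightly different rule, and a reader of the tables cannot tell how an event on the morning of Day 0 was counted.

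The interim analysis covers 7 treated subjects (SAP 6.1), and its report goes to FDA (SAP 6.4). At that size a single subject is visible in any percentage.

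**Working it through.** The plan states no figure on this point, so there is none to reproduce. The check applies the written rules to dates.

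**1. Table 2.2 applied literally.** Assumed first dose: 20 June 2019.

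| Recorded start | Recorded end | Flag under Table 2.2 | Shown by the end date |
|---|---|---|---|
| Day unknown, June 2019 | 10 June 2019 | TEAE | Over before first dose |
| Day and month unknown, 2019 | 15 May 2019 | TEAE | Over before first dose |
| Day unknown, May 2019 | any | not TEAE | No conflict |

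The fault arises only where the known part of the start date cannot itself place onset before the first dose. In the first two rows the flag contradicts the table's own meaning of a non-TEAE. An event flagged in this way with onset in the first-dose month also satisfies the table's condition for occurrence up to Week 4, so it enters that set of tables too.

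**2. How often, given a pre-dose AE that ended before dosing.** With only the day missing, the flag is wrong when true onset, k days before the first dose, lies in the same calendar month. For k up to 28, each month has exactly k dates for which it does not, so over a 365-day year

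share(k) = 1 - 12k/365.

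- Onset at SV2, k = 7: 1 - 84/365 = 77.0%.
- Onset at SV2, k = 4: 1 - 48/365 = 86.8% (86.9% over 2018 to 2021: 1 - 192/1461).
- Onset uniform over Day -42 to -1 (assumed): the shares for k = 1 to 28 sum to 28 - 12 × 406/365 = 14.652. For k = 29 there are 18 qualifying dates (4 in the 30-day months, 14 in the 31-day months), for k = 30 there are 7, and beyond that none, which adds 25/365 = 0.068. Then 14.720/42 = 35.0%.

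With the month also missing, the same uniform assumption gives 1 - 21.5/365 = 94.1%. With the year missing it is 100%.

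All these shares are conditional on a pre-dose AE with an incomplete start date and an end before the first dose. The documents do not say how often that combination occurs.

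**3. Weight of one subject.** 1/7 = 14.3 points at the interim analysis; 1/30 = 3.3 points at the planned enrolment. At N = 7 one non-serious event is enough to meet the 5% threshold of Table 14.3.1.10.1.

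**4. Day 0 events under each definition.**

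| Event | SAP 9.2 | Footnotes | Protocol 8.8.3, first-application day = Day 0 | Protocol 8.8.3, first-application day = Day 1 |
|---|---|---|---|---|
| Day 0, before application | TEAE | not TEAE | not TEAE | TEAE |
| Day 0, after application | TEAE | TEAE | not TEAE | TEAE |
| Next day | TEAE | TEAE | TEAE | TEAE |

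Within the SAP the only disagreement is the first row. The last column uses the SAP 7 study-day formula (event date minus reference date, plus 1), under which the day of first application is study day 1.

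**The case against.** **The default is conservative.** Table 2.2 can add pre-dose events to the TEAE count but does not remove a post-dose event. SAP 9.2 takes the worst case for missing severity and relationship in the same spirit. This stands as to direction. It justifies the default where timing is unknown, but not where a recorded end date settles the question.

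**The comparison with medical history and medication is imperfect.** Those records are classified by stop date, whereas a TEAE is defined by onset. That is correct, so the comparison shows only that the SAP already accepts partial end dates as evidence. The point rests instead on Table 2.2's own description of a non-TEAE: an event that ended before treatment must also have begun before it.

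**The listings reveal such cases.** SAP 6.3 keeps unimputed dates in listings, and Listing 16.2.7.1 shows start and end beside the TEAE flag. With 7 subjects a contradiction would be noticed. This limits the harm, but the tables would still carry the wrong count.

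**The protocol may not differ at all.** A reader might infer that protocol 8.8.3 excludes reactions on the day of the supervised first application, and that SAP 14 omits a change it should declare. The documents do not support this. Protocol 8.8.3 puts Baseline in brackets after Day 1, a day after the first application could hardly be Baseline, and SAP 7 numbers the first-application day as study day 1. On that reading protocol 8.8.3 and SAP 9.2 are the same rule. What remains is an ambiguity against the protocol's Day 0 numbering.

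**Conclusion.** The point holds as a minor one. Table 2.2 lacks an end-date condition and can flag as treatment-emergent an AE that the recorded data show was over before the first application. The error only over-counts TEAEs and should be rare.

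Where the day is missing and the AE was truly pre-dose, the flag is wrong in about 35% of cases under the assumed uniform onset over Day -42 to -1, and in 77% to 87% if onset is at SV2. The higher range might be read as a general misclassification rate; it is not, because it applies only to onset at that visit. The 14.3 points at N = 7 is the weight of any one subject, not an expected bias. The HPA, calcium and PK summaries do not use this flag.

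The definitions in SAP 9.2 and in the footnotes differ only for Day 0 events that begin before the application. Protocol 8.8.3 is unclear rather than shown to conflict.

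**What to change.** 1. In each row of Table 2.2 add: *unless the complete or partial end date shows that the AE ended before the first application*. Every AE whose end date proves it was pre-dose then becomes a non-TEAE, and the default stays for the rest.
2. Use one definition in SAP 9.2, the Table 14.3.1.1 footnote and Listings 16.2.7.1 to 16.2.7.4: onset date and time at or after the first application, with a Day 0 onset and missing time counted as TEAE. Listing 16.2.7.1 already carries AE times. Table 2.2 has no row for a complete date with the time missing, so this case needs to be stated.
3. Note in SAP 14 how Day 1 (Baseline) in protocol 8.8.3 is interpreted.

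The cost is SAP wording and one extra programming condition. No new data are needed.
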